9.4.2. Safety Analyses

AEs will be coded using the MedDRA coding dictionary and summarized by preferred term and treatment group. SAEs pre-treatment *and* AEs and SAEs on-treatment, during active treatment, and post-treatment will be summarized separately. Separate summaries will be provided for all AEs, IP-related AEs, SAEs, events of special interest (including systemic reactions and local injection site reactions) and for AEs leading to permanent discontinuation of IP or withdrawal from the study. All laboratory parameters for clinical chemistry and hematology will be summarized and tabulated.

Each ECG parameter at every assessed time point will be summarized using summary statistics. Summary statistics of QT interval corrected for heart rate according to Fridericia’s formula (QTcF) and QT interval corrected for heart rate according to Bazett’s formula (QTcB) as well as change from baseline value will be presented by visit.

Summary statistics of pulse rate and systolic and diastolic blood pressure will be presented by visit.

Immunogenicity will be summarized using appropriate descriptive statistics.

9.4.3. Pharmacokinetic Analyses

Blood samples will be collected to determine mepolizumab plasma concentrations (Section 7.5). Sparse blood sampling is being implemented in this study. The mepolizumab plasma concentrations from this study will be evaluated using the population PK model developed based on previous mepolizumab data collected during

mepolizumab clinical development. The analysis will be conducted using an appropriate software and will allow the determination for example of the population and/or individual systemic exposure, apparent volume of distribution and apparent clearance as well as characterize the between- and within subject variability. The effect of subjects' characteristics such as, for example, body weight, age, gender, serum creatinine on mepolizumab systemic exposure will also be explored in order to explain the inter-subject variability in drug exposure. Pharmacokinetic data will be presented in graphical and/or tabular form and will be summarized descriptively.

Further details of the analysis will be described in the RAP.

9.4.4. Pharmacodynamic Analyses

Ratio to baseline in blood eosinophil count will be compared between treatments using a mixed model repeated measures analysis adjusting for the covariates of baseline blood eosinophil count, baseline OCS dose and region. Values below the lower limit of quantification will be imputed as half the lower limit of quantification prior to analysis. Data will be log-transformed prior to analysis. Visit will be fitted as a categorical variable with the effect of treatment group and baseline eosinophil count varying at each visit (i.e., visit by baseline and visit by treatment group interactions will also be included in the model).

9.4.5. Other Analyses

Full details of the analyses to be performed on all exploratory endpoints will be given in the RAP.

If genetic analysis is warranted, a separate research analysis plan will be drafted (Section [12.3](#)).

If biomarker analysis is warranted, a separate research analysis plan will be drafted (Section [7.10](#)).

10. STUDY GOVERNANCE CONSIDERATIONS

10.1. Posting of Information on Publicly Available Clinical Trial Registers

Study information from this protocol will be posted on publicly available clinical trial registers before enrollment of subjects begins.

10.2. Regulatory and Ethical Considerations, Including the Informed Consent Process

Prior to initiation of a site, GSK will obtain favourable opinion/approval from the appropriate regulatory agency to conduct the study in accordance with ICH Good Clinical Practice (GCP) and applicable country-specific regulatory requirements.

The study will be conducted in accordance with all applicable regulatory requirements, and with GSK policy.

The study will also be conducted in accordance with ICH Good Clinical Practice (GCP), all applicable subject privacy requirements, and the guiding principles of the current version of the Declaration of Helsinki. This includes, but is not limited to, the following:

- IRB/IEC review and favorable opinion/approval of the study protocol and amendments as applicable
- Obtaining signed informed consent
- Investigator reporting requirements (e.g. reporting of AEs/SAEs/protocol deviations to IRB/IEC)
- GSK will provide full details of the above procedures, either verbally, in writing, or both.
- Signed informed consent must be obtained for each subject prior to participation in the study
- The IEC/IRB, and where applicable the regulatory authority, approve the clinical protocol and all optional assessments, including genetic research.
- Optional assessments (including those in a separate protocol and/or under separate informed consent) and the clinical protocol should be concurrently submitted for approval unless regulation requires separate submission.
- Approval of the optional assessments may occur after approval is granted for the clinical protocol where required by regulatory authorities. In this situation, written approval of the clinical protocol should state that approval of optional assessments is being deferred and the study, with the exception of the optional assessments, can be initiated.

10.3. Quality Control (Study Monitoring)

- In accordance with applicable regulations including GCP, and GSK procedures, GSK monitors will contact the site prior to the start of the study to review with the site staff the protocol, study requirements, and their responsibilities to satisfy regulatory, ethical, and GSK requirements.
- When reviewing data collection procedures, the discussion will also include identification, agreement and documentation of data items for which the CRF will serve as the source document.

GSK will monitor the study and site activity to verify that:

- Data are authentic, accurate, and complete.
- Safety and rights of subjects are being protected.
- Study is conducted in accordance with the currently approved protocol and any other study agreements, GCP, and all applicable regulatory requirements.

- The investigator and the head of the medical institution (where applicable) agrees to allow the monitor direct access to all relevant documents

10.4. Quality Assurance

- To ensure compliance with GCP and all applicable regulatory requirements, GSK may conduct a quality assurance assessment and/or audit of the site records, and the regulatory agencies may conduct a regulatory inspection at any time during or after completion of the study.
- In the event of an assessment, audit or inspection, the investigator (and institution) must agree to grant the advisor(s), auditor(s) and inspector(s) direct access to all relevant documents and to allocate their time and the time of their staff to discuss the conduct of the study, any findings/relevant issues and to implement any corrective and/or preventative actions to address any findings/issues identified.

10.5. Study and Site Closure

- Upon completion or premature discontinuation of the study, the GSK monitor will conduct site closure activities with the investigator or site staff, as appropriate, in accordance with applicable regulations including GCP, and GSK Standard Operating Procedures.
- GSK reserves the right to temporarily suspend or prematurely discontinue this study at any time for reasons including, but not limited to, safety or ethical issues or severe non-compliance. For multicenter studies, this can occur at one or more or at all sites.
- If GSK determines such action is needed, GSK will discuss the reasons for taking such action with the investigator or the head of the medical institution (where applicable). When feasible, GSK will provide advance notification to the investigator or the head of the medical institution, where applicable, of the impending action.
- If the study is suspended or prematurely discontinued for safety reasons, GSK will promptly inform all investigators, heads of the medical institutions (where applicable) and/or institution(s) conducting the study. GSK will also promptly inform the relevant regulatory authorities of the suspension or premature discontinuation of the study and the reason(s) for the action.
- If required by applicable regulations, the investigator or the head of the medical institution (where applicable) must inform the IRB/IEC promptly and provide the reason for the suspension or premature discontinuation.

10.6. Records Retention

- Following closure of the study, the investigator or the head of the medical institution (where applicable) must maintain all site study records (except for those required by local regulations to be maintained elsewhere), in a safe and secure location.
- The records must be maintained to allow easy and timely retrieval, when needed (e.g., for a GSK audit or regulatory inspection) and must be available for review in

conjunction with assessment of the facility, supporting systems, and relevant site staff.

- Where permitted by local laws/regulations or institutional policy, some or all of these records can be maintained in a format other than hard copy (e.g., microfiche, scanned, electronic); however, caution needs to be exercised before such action is taken.
- The investigator must ensure that all reproductions are legible and are a true and accurate copy of the original and meet accessibility and retrieval standards, including re-generating a hard copy, if required. Furthermore, the investigator must ensure there is an acceptable back-up of these reproductions and that an acceptable quality control process exists for making these reproductions.
- GSK will inform the investigator of the time period for retaining these records to comply with all applicable regulatory requirements. The minimum retention time will meet the strictest standard applicable to that site for the study, as dictated by any institutional requirements or local laws or regulations, GSK standards/procedures, and/or institutional requirements.
- The investigator must notify GSK of any changes in the archival arrangements, including, but not limited to, archival at an off-site facility or transfer of ownership of the records in the event the investigator is no longer associated with the site.

10.7. Provision of Study Results to Investigators, Posting of Information on Publicly Available Clinical Trials Registers and Publication

Where required by applicable regulatory requirements, an investigator signatory will be identified for the approval of the clinical study report. The investigator will be provided reasonable access to statistical tables, figures, and relevant reports and will have the opportunity to review the complete study results at a GSK site or other mutually-agreeable location.

GSK will also provide the investigator with the full summary of the study results. The investigator is encouraged to share the summary results with the study subjects, as appropriate.

GSK will provide the investigator with the randomization codes for their site only after completion of the full statistical analysis.

The procedures and timing for public disclosure of the results summary and for development of a manuscript for publication will be in accordance with GSK Policy.

A manuscript will be progressed for publication in the scientific literature if the results provide important scientific or medical knowledge.

10.8. Independent Data Monitoring Committee

An IDMC will be utilized in this study to ensure external objective medical and/or statistical review of safety data in order to protect the ethical and safety interests of subjects and to protect the scientific validity of the study. The schedule of any planned interim analysis and the analysis plan for IDMC review is described in the charter.

12. APPENDICES

12.1. Appendix 1: Abbreviations and Trademarks

Abbreviations

ACQ	Asthma Control Questionnaire
ADA	Anti-drug antibody
AE	Adverse Event
ALT	Alanine transaminase
ANCA	anti-neutrophil cytoplasmic antibodies
AST	Aspartate transaminase
BP	Blood pressure
CONSORT	Consolidated Standards of Reporting Trials
CPK	Creatine phosphokinase
CRF	Case Report Form
C-RTS	Clinician-rated overall Response to Therapy score
CUP	Compassionate Use Program
CV	Cardiovascular
DNA	Deoxyribonucleic acid
ECG	Electrocardiogram
eCRF	Electronic case report form
eDiary	Electronic diary
EGPA	Eosinophilic Granulomatosis with Polyangiitis
EoE	Eosinophilic Esophagitis
EW	Early Withdrawal
FAAN	Food Allergy and Anaphylaxis Network
FRP	Female of reproductive potential
FEV ₁	Forced Expiratory Volume in one second
FISH	Fluorescence in situ hybridization
F/P	Fip1-like1-Platelet Derived Growth Factor Receptor α (FIP1L1-PDGFR α)
FSH	Follicle stimulating hormone
FVC	Forced Vital Capacity
GCP	Good Clinical Practice
GCSP	Global Clinical Safety and Pharmacovigilance
GI	Gastrointestinal
GSK	GlaxoSmithKline
HBsAg	Hepatitis B Surface Antigen
hCG	human chorionic gonadotrophin
HCRU	Healthcare resource utilization
HCV	Hepatitis C Virus
HES	Hypereosinophilic Syndrome
HF	Heart failure
HIV	Human Immunodeficiency Virus
HPLC	High performance liquid chromatography

HRQoL	Health-related quality of life
HRT	Hormone replacement therapy
IB	Investigator's Brochure
ICU	Intensive care unit
IDMC	Independent data monitoring committee
IEC	Independent Ethics Committee
Ig	Immunoglobulin
IL	Interleukin
INF α	Interferon alpha
INR	International normalized ratio
IP	Investigational Product
IRB	Institutional review board
IRT	Interactive response technology
ITT	Intent-to-Treat
IV	Intravenous(ly)
LABA	Long-acting beta ₂ -agonist
LDH	Lactate dehydrogenase
L-HES	Lymphocytic hypereosinophilic syndrome
mAb	Monoclonal antibody
MedDRA	Medical Dictionary for Regulatory Activities
mg	milligrams
M-HES	Myeloproliferative hypereosinophilic syndrome
MSAS-SF	Memorial Symptom Assessment Scale-Short Form
MSDS	Material Safety Data Sheet
msec	millisecond
NAB	Neutralizing antibodies
NIAID	National Institute of Allergy and Infectious Disease
NYHA	New York Heart Association
OCS	Oral corticosteroid
OLE	Open-label extension
PCR	Polymerase chain reaction
PCSA	Placebo-controlled severe asthma
PD	Pharmacodynamics
PEF	Peak expiratory flow
PK	Pharmacokinetics
PMS	Post marketing surveillance
PP	Per protocol
PRO	Patient reported outcome
PROMIS	Patient Reported Outcome Measurement Information System
QTcB	QT interval corrected for heart rate according to Bazett's formula
QTcF	QT interval corrected for heart rate according to Fridericia's formula
RAP	Reporting and Analysis Plan
RBC	Red blood cell

RNA	Ribonucleic acid
RTS	Response to Therapy Score
SABA	Short-acting beta ₂ -agonist
SAE	Serious Adverse Event
SC	Subcutaneous(ly)
SDAC	Statistical analysis data center
SOC	System Organ Class
SoC	Standard of care
SRM	Study reference manual
SSR	Subject-Rated Symptom Severity
URTI	Upper respiratory tract infection
WBC	White blood cell
Wks	Weeks

Trademark Information

Trademarks of the GlaxoSmithKline group of companies
NONE

Trademarks not owned by the GlaxoSmithKline group of companies
None

12.2. Appendix 2: Phase III-IV liver chemistry stopping and monitoring criteria, and required actions and follow-up assessments

Phase III-IV liver chemistry stopping criteria

Liver Chemistry Stopping Criteria – Liver Stopping Event	
ALT absolute	Both ALT \geq 8xULN and \geq 2X baseline value
ALT Increase	Both ALT \geq 3xULN and \geq 1.5x baseline value that persists for \geq 4 weeks
Bilirubin ^{1,2}	ALT \geq 3xULN and bilirubin \geq 2xULN (>35% direct bilirubin)
INR ²	ALT \geq 3xULN and INR>1.5, if INR measured
Cannot Monitor	Both ALT \geq 3xULN and \geq 1.5x baseline value and cannot be monitored weekly for \geq 4 weeks
Symptomatic ³	Both ALT \geq 3xULN and \geq 1.5x baseline value associated with symptoms (new or worsening) believed to be related to liver injury or hypersensitivity
Required Actions and Follow up Assessments following ANY Liver Stopping Event	
Actions	Follow Up Assessments

 • Immediately discontinue study treatment. • Report the event to GSK within 24 hours. • Complete the liver event CRF and complete SAE data collection tool if the event also meets the criteria for an SAE². • Perform liver event follow up assessments. • Monitor the subject until liver chemistries resolve, stabilize, or return to within baseline (see MONITORING below). • Do not restart/rechallenge subject with study treatment unless allowed per protocol and GSK Medical Governance approval is granted. • If restart/rechallenge not allowed or not granted, permanently discontinue study treatment and may continue subject in the study for any protocol specified follow up assessments. 
MONITORING:
 
For bilirubin or INR criteria:
 
 • Repeat liver chemistries (include ALT, AST, alkaline phosphatase, bilirubin) and perform liver 	
 • Viral hepatitis serology⁴ • Obtain INR and recheck with each liver chemistry assessment until the transaminases values show downward trend. • Only in those with underlying chronic hepatitis B at study entry (identified by positive hepatitis B surface antigen) quantitative hepatitis B DNA and hepatitis delta antibody⁵. • Blood sample for pharmacokinetic (PK) analysis, obtained within 1 week of the liver event⁶. • Serum creatine phosphokinase (CPK) and lactate dehydrogenase (LDH). • Fractionate bilirubin, if total bilirubin \geq2xULN. • Obtain complete blood count with differential to assess eosinophilia. 
Note: To ensure investigators remain blinded to eosinophil count, as for all other blood count tests after randomization, sites will only be sent absolute lymphocyte, monocyte, neutrophil, and basophil counts. The


event follow up assessments within 24 hrs.
 
 • Monitor subjects twice weekly until liver chemistries resolve, stabilize or return to within baseline. • A specialist or hepatology consultation is recommended. 
For All other criteria:
 
 • Repeat liver chemistries (include ALT, AST, alkaline phosphatase, bilirubin) and perform liver event follow up assessments within 24-72 hrs. • Monitor subjects weekly until liver chemistries resolve, stabilize or return to within baseline. 	
complete blood count with differential (including eosinophil count will be available after the subject's treatment has been unblinded.
 
 • Record the appearance or worsening of clinical symptoms of liver injury, or hypersensitivity, on the AE report form. • Record use of concomitant medications on the concomitant medications report form including acetaminophen, herbal remedies, other over the counter medications. • Record alcohol use on the liver event alcohol intake case report form. 
For bilirubin or INR criteria:
 
 • Anti-nuclear antibody, anti-smooth muscle antibody, Type 1 anti-liver kidney microsomal antibodies, and quantitative total immunoglobulin G (IgG or gamma globulins) • Serum acetaminophen adduct HPLC assay (quantifies potential acetaminophen contribution to liver injury in subjects with definite or likely acetaminophen use in the preceding week [James, 2009]). NOTE: not required in China. • Liver imaging (ultrasound, magnetic resonance, or computerised tomography) and /or liver biopsy to evaluate liver disease: complete Liver Imaging and/or Liver Biopsy CRF forms
---	--

1. Serum bilirubin fractionation should be performed if testing is available. If serum bilirubin fractionation is not immediately available, discontinue study treatment for that subject if ALT \geq 3xULN **and** bilirubin \geq 2xULN. Additionally, if serum bilirubin fractionation testing is unavailable, **record presence of detectable urinary bilirubin on dipstick**, indicating direct bilirubin elevations and suggesting liver injury.
2. All events of ALT \geq 3xULN **and** bilirubin \geq 2xULN (>35% direct bilirubin) or ALT \geq 3xULN **and** INR>1.5, if INR measured which may indicate severe liver injury (possible 'Hy's Law'), **must be reported as an SAE (excluding studies of hepatic impairment or cirrhosis)**; INR measurement is not required and the threshold value stated will not apply to subjects receiving anticoagulants
3. New or worsening symptoms believed to be related to liver injury (such as fatigue, nausea, vomiting, right upper quadrant pain or tenderness, or jaundice) or believed to be related to hypersensitivity (such as fever, rash or eosinophilia)
4. Includes: Hepatitis A IgM antibody; Hepatitis B surface antigen and Hepatitis B Core Antibody (IgM); Hepatitis C RNA; Cytomegalovirus IgM antibody; Epstein-Barr viral capsid antigen IgM antibody (or if unavailable, obtain heterophile antibody or monospot testing); Hepatitis E IgM antibody
5. If hepatitis delta antibody assay cannot be performed, it can be replaced with a PCR of hepatitis D RNA virus (where needed) [Le Gal, 2005].
6. PK sample may not be required for subjects known to be receiving placebo or non-GSK comparator treatments.) Record the date/time of the PK blood sample draw and the date/time of the last dose of study treatment prior to blood sample draw on the CRF. If the date or time of the last dose is unclear, provide the subject's best approximation. If the date/time of the last dose cannot be approximated OR a PK sample cannot be collected in the time period indicated above, do not obtain a PK sample. Instructions for sample handling and shipping are in the SRM.

Phase III-IV liver chemistry increased monitoring criteria with continued therapy

Liver Chemistry Increased Monitoring Criteria – Liver Monitoring Event	
Criteria	Actions
ALT \geq 3xULN and \geq 1.5x baseline value but ALT <8x ULN and < 2x baseline value and bilirubin <2xULN without symptoms believed to be related to liver injury or hypersensitivity, and who can be monitored weekly for 4 weeks.	
 • Notify the GSK medical monitor within 24 hours of learning of the abnormality to discuss subject safety. • Subject can continue study treatment. • Subject must return weekly for repeat liver chemistries (ALT, AST, alkaline phosphatase, bilirubin) until they resolve, stabilise or return to within baseline. • If at any time subject meets the liver chemistry stopping criteria, proceed as described above • If, after 4 weeks of monitoring, ALT <3xULN and <1.5 X baseline value, and bilirubin <2xULN, monitor subjects twice monthly until liver chemistries normalize or return to within baseline

References

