5.2. Exclusion Criteria

A subject will not be eligible for inclusion in this study if any of the following criteria apply:

CONCURRENT CONDITIONS/MEDICAL HISTORY (INCLUDES LIVER FUNCTION AND QTc INTERVAL)

1. Life-threatening HES or life-threatening HES co-morbidities: Imminently life-threatening HES disease severity such that the likelihood of death is high unless the course of the disease is interrupted within 12 weeks prior to randomization (Visit 2).
2. Other concurrent medical conditions that may affect the subject's safety:

Subjects who have known, pre-existing, *clinically significant* endocrine, autoimmune, metabolic, neurological, renal, gastrointestinal, hepatic, hematological, respiratory or any other system abnormalities that are not associated with HES and are uncontrolled with standard treatment.
3. Eosinophilia of unknown clinical significance
4. 12-lead ECG finding:

QTc > 450 msec *or* QTc > 480 msec in subjects with bundle branch block

An abnormal ECG finding from the 12-lead ECG conducted at Visit 1 if considered to be clinically significant and would impact the subject's participation during the study based on the evaluation of the Investigator.

NOTE: 12-lead ECG results at screening (Visit 1) with the over-read by the centralized independent cardiologist must be received prior to assessing eligibility at Visit 2 by the Investigator.
5. Subjects with documented history of any clinically significant cardiac damage prior to screening (Visit 1) that, in the opinion of the investigator, would impact the

subject's participation during the study.

6. Liver abnormality/disease:

- ALT >2.5xULN *or* ALT>5xULN if documented HES with liver manifestations
- Bilirubin >1.5xULN (isolated bilirubin >1.5xULN is acceptable if bilirubin is fractionated and direct bilirubin <35%)
- Current active liver or biliary disease (with the exception of Gilbert's syndrome or asymptomatic gallstones or otherwise stable chronic liver disease per investigator assessment).

NOTE: Stable chronic liver disease should generally be defined by the absence of ascites, encephalopathy, coagulopathy, hypoalbuminaemia, oesophageal or gastric varices, or persistent jaundice, or cirrhosis.

NOTE: Chronic stable hepatitis B and C (e.g., presence of hepatitis B surface antigen (HBsAg) or positive hepatitis C antibody test result at screening or within 3 months prior to first dose of study treatment) are acceptable if subject otherwise meets entry criteria.

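### As worded, the liver increased-monitoring row is empty for baseline ALT up to 1.5xULN, so an asymptomatic first ALT of 3 to <8xULN can meet no row

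*Protocol*

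**What the plan says.** Protocol Appendix 2 (Section 12.2) has two tables. The first lists six ways to reach a liver stopping event; the second has one row for increased monitoring while treatment continues.

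- **ALT absolute (stop):** "Both ALT \geq 8xULN and \geq 2X baseline value".
- **ALT increase (stop):** "Both ALT \geq 3xULN and \geq 1.5x baseline value that persists for \geq 4 weeks".
- **Cannot monitor (stop):** "Both ALT \geq 3xULN and \geq 1.5x baseline value and cannot be monitored weekly for \geq 4 weeks".
- **Bilirubin, INR, symptomatic (stop):** each starts from ALT of at least 3xULN and adds its own further condition.
- **Increased monitoring (continue):** ALT of at least 3xULN and at least 1.5x baseline, "but ALT <8x ULN and < 2x baseline value and bilirubin <2xULN without symptoms", in a subject who can attend weekly for 4 weeks. The attached actions are notice to the medical monitor within 24 hours and weekly repeat liver chemistries.

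Exclusion criterion 6 in Section 5.2 bars "ALT >2.5xULN *or* ALT>5xULN if documented HES with liver manifestations". Baselines up to 2.5xULN are therefore eligible, and up to 5xULN in subjects with liver involvement. Section 5.4.1 presents Figure 2 as the algorithm for stopping and monitoring events. The figure's content is missing from the text available for this review.

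**The concern.** The monitoring row should catch elevations that have passed the 3xULN and 1.5x-baseline floor but do not yet call for an immediate stop. The ALT-absolute stop is a joint condition, so failing it means that *either* part fails. The monitoring row instead requires that *both* parts fail. The two rows therefore leave a region between them, and for subjects with a normal or mildly raised baseline that region takes up the whole of 3 to <8xULN.

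The cannot-monitor row makes the inconsistency visible. It applies from the same floor and has no 2x-baseline cap, which implies that other subjects at those values are being monitored weekly. Read literally, a subject with baseline 1xULN and ALT 5xULN who cannot attend weekly is stopped, while an identical subject who can attend weekly is given no monitoring instruction.

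At stake are prompt notice and weekly follow-up for an isolated first elevation, and consistent classification across sites. The SAP plans a summary of liver monitoring and stopping event reporting (Section 11.2 and Table 4.52), so an ambiguous definition of a monitoring event feeds a planned safety output.

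**Working it through.** No published figure has to be reproduced; this is a check of inequalities. Let *b* be baseline ALT and *a* on-study ALT, both in multiples of ULN.

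**Inputs** (Appendix 2, and Section 5.2 for the range of *b*)

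1. Floor: *a* ≥ 3 and *a* ≥ 1.5*b*, i.e. *a* ≥ max(3, 1.5*b*).
2. Monitoring row: the floor, plus *a* < 8 and *a* < 2*b*. So max(3, 1.5*b*) ≤ *a* < min(8, 2*b*).
3. ALT-absolute stop: *a* ≥ 8 and *a* ≥ 2*b*, i.e. *a* ≥ max(8, 2*b*).
4. Eligible *b*: up to 2.5, or up to 5 with documented liver HES.

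**When the monitoring row is empty.** It needs 3 < 2*b*, so *b* > 3/2 = 1.5. (It also needs 1.5*b* < 8, i.e. *b* < 5.33, which every eligible baseline satisfies.) For *b* ≤ 1.5, 2*b* ≤ 3, so any *a* ≥ 3 is already at least 2*b* and no value qualifies. An exact search in steps of 0.01xULN agrees: the first baseline with any qualifying value is 1.51, where the row covers only 3.00 and 3.01.

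**Values at or above the floor that meet neither row**

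| Baseline *b* | Monitoring row | ALT-absolute stop from | Neither row |
|---|---|---|---|
| 0.5, 1.0 or 1.5 | empty | 8 | 3 to <8 |
| 2.0 | 3 to <4 | 8 | 4 to <8 |
| 2.5 | 3.75 to <5 | 8 | 5 to <8 |
| 3.0 | 4.5 to <6 | 8 | 6 to <8 |
| 4.0 | 6 to <8 | 8 | none |
| 4.5 | 6.75 to <8 | 9 | 8 to <9 |
| 5.0 | 7.5 to <8 | 10 | 8 to <10 |

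Below *b* = 4 the gap arises because *a* has passed 2*b* before reaching 8. Above *b* = 4 it arises because *a* has passed 8 before reaching 2*b*. An ALT of exactly 8xULN meets the stop whenever *b* ≤ 4, so the upper end of the first gap is <8.

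**One subject through all seven rows.** Take *b* = 1, first *a* = 5, no symptoms, bilirubin <2xULN, no INR criterion met, weekly visits feasible.

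- Monitoring: 5 ≥ 3, 5 ≥ 1.5 and 5 < 8 hold, but 5 < 2 fails. Not met.
- ALT absolute: 5 ≥ 8 fails.
- ALT increase: the values qualify, but 4 weeks have not passed.
- Bilirubin, INR, symptomatic: the added condition is absent.
- Cannot monitor: the values qualify, but weekly visits are possible.

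No row is met that day, so no listed action follows.

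**Alternative reading.** If the clause after *but* is taken to mean *not meeting the ALT-absolute row*, monitoring becomes every value at or above the floor that does not meet that stop. The gap then closes by construction. The printed wording does not say this.

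**The case against.** The arithmetic on the printed text is not in dispute. The case on the other side concerns how much follows from it, and much of that case stands.

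- A reader might infer that these subjects have no liver follow-up or stopping rule at all. The documents do not support that. Every subject with *b* ≤ 1.5 and ALT 3 to <8xULN satisfies the ALT part of the increase and cannot-monitor rows, and the symptom, bilirubin and INR rows remain open. Chemistry is scheduled every four weeks from Week 4 to Week 32 (Table 2), so a persistent rise can be found at a later scheduled visit. Clinically significant laboratory changes may also be reported as adverse events.
- A reader might infer that liver events in general would be captured unevenly. The SAP's stopping-event listings (43 and 44) take in every subject meeting the criteria, whether or not the site completed the liver pages, and plots of maximum ALT against baseline ALT and against bilirubin are planned regardless. That backstop does not extend to monitoring events, so uneven capture is plausible only for them.
- A reader might infer that most enrolled subjects are affected. Neither document gives a baseline ALT distribution, so the share with *b* ≤ 1.5 is unknown.
- A reader might want each ALT value to fall in exactly one row. That is not a sound target: the stopping rows overlap by design, and subjects are expected to pass from monitoring to stopping.
- Figure 2 may state the rule differently, and a sensible investigator may adopt the alternative reading. Either would soften the practical effect, but it would also mean that the table conflicts with the figure or is applied differently between sites.

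**Conclusion.** The drafting inconsistency is real. On the literal text the monitoring row cannot be met by any subject with baseline ALT at or below 1.5xULN. For an asymptomatic first elevation of 3 to <8xULN, under the bilirubin, INR and visit conditions above, no action is listed on the day. Narrower gaps remain at other eligible baselines, as tabulated, with none at exactly 4xULN.

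The loss is limited to the 24-hour notice, the weekly repeats and uniform classification of monitoring events. No efficacy analysis is affected.

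The conclusion is firm for the wording of the two tables. It is less firm for what sites would do, because Figure 2 could not be read. It assumes that the baseline in Appendix 2 is a pre-treatment ALT within the Section 5.2 limits. It assumes nothing about how common any baseline value is.

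**What to change.** The sponsor must reconcile the upper bound of the monitoring row with the ALT-absolute stopping row in Appendix 2, and both with Figure 2. After the change, no ALT at or above 3xULN and 1.5x baseline should be left without a listed action. The stopping rows may go on overlapping. Which rule applies in the region now uncovered is for the sponsor's safety physicians to decide; no threshold is proposed here. The SAP's summary of monitoring events should then follow the reconciled definition.

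The cost is a change of protocol wording and a clarification memo to sites. The reconciliation itself adds no new kind of test.
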